### 7.8.1.2 *Adverse Events*

All AEs between enrollment/randomization to the EOS visit will be recorded in source data and eCRF, whether or not considered study drug-related. All AEs that are possibly or probably related to study drug will be followed until resolution or database lock, whichever occurs first. Also, the sign, symptom, or disease present before the baseline safety assessment are only considered AEs if they worsen after this point. Any AEs already documented at a previous assessment and designated as ongoing should be reviewed at subsequent visits as necessary. If these have resolved, this should be documented. The Investigator should report all AEs on the AE page(s) of the eCRF and source documents, regardless of seriousness, severity, and causality. Whenever possible, an AE will be reported using a diagnostic term, (e.g., “common cold” or “upper respiratory infection” rather than “runny nose, cough, mild fever”) and should be described with the attributes described in [Section 7.7.1.1](#).

### 7.8.1.3 *Serious Adverse Events*

Each AE will be assessed to determine whether it meets seriousness criteria ([Section 7.7.1.2](#)). If the AE is considered serious the Investigator must report this event to the Sponsor or delegate. The Sponsor or delegate will report the event to the IRB/EC according to relevant standard operating procedures (SOPs). Serious adverse events occurring from the time of signed informed consent to the EOS visit or 7 days after the last administration of study drug (whichever occurs later) will be recorded in source and electronic data capture. All serious, treatment-related adverse events, regardless of the time of onset after treatment, should be reported. All information about SAEs will be collected and reported via the SAE form and sent by email message (contact information will be contained in the Investigator site file). At a minimum, the initial report should include the following information:

- Event
- Seriousness criteria
- Protocol number
- Participant number and year of birth
- Study drug (blinded for Part B unless unblinding is required for medical management)
- Reporter name and contact information

In the case of a “minimum report” (one that solely comprises the information bulleted above), a more detailed Follow-Up report should be sent as soon as more information becomes available but no later than 7 calendar days after the date of the initial report. Each SAE should be followed up until resolution or stabilization and for reported deaths, the Investigator should supply Sponsor, or designee, and the IRB/EC with any additional requested information (e.g., autopsy reports and terminal medical reports), if available. The original SAE form should be kept at the study site. The Investigators will be responsible for determining and in turn, reporting SAEs to the Sponsor. The Sponsor, or designee, will be responsible for reporting SAEs to regulatory authorities according to the applicable regulatory requirements. The Sponsor, or designee, will be responsible for completing the safety reports and for notifying the relevant authorities of any SAE as outlined in the International Council for Harmonisation (ICH) Guidelines and per local regulatory requirements.

## 7.8.2 Prompt Reporting of Serious Adverse Events

Any SAE, occurring in a participant receiving treatment or if the Investigators become aware of any SAE post-treatment during the EOS visit, must be reported by the Investigators to the Medical Monitor within 24 hours even if the SAE does not appear to be medication-related. An emailed copy of the SAE form, in addition to other related information should be sent to the appropriate contact as outlined in the Investigator site file. Additionally, it may be necessary for the Medical Monitor or Sponsor, or delegate, to directly communicate with the Investigators if additional information is required.

### 7.8.2.1 Follow-Up of Adverse Events

All AEs will be followed to a satisfactory resolution, until it becomes stable, or until it can be explained by another known cause(s) (i.e., concurrent condition or medication) and clinical judgment indicates that further evaluation is not warranted.

### Suspected Unexpected Serious Adverse Reactions (SUSARs)

The Sponsor, or designee, is responsible for the reporting of SUSARs in accordance with regulatory guidelines. An AE will be considered unexpected if the nature, severity, frequency of the event is not consistent with the risk information previously described for the IMP. The 'expectedness' for any SAE will be determined against the reference safety information (RSI) included in the IB.

A list of expected potential adverse reactions are provided in the IB.

## 7.8.3 Special Considerations

### 7.8.3.1 Pregnancy of Female Participant and/or of Female Partner of Male Participant

Details of all pregnancies in female participants and female partners of male participants will be collected after the start of the study until the end of the study. The Investigators should report pregnancy to the Sponsor or designee within 24 hours after learning of the pregnancy.

If a pregnancy is reported, the Investigator should contact the designated individual(s) following the pregnancy notification process and record information related to the pregnancy on the designated pregnancy form provided.

While pregnancy itself is not considered to be an AE or SAE, any pregnancy complication or elective termination of a pregnancy for medical reasons will be reported as an AE or SAE.

The event meets the SAE criterion only if it results in a spontaneous abortion, congenital anomaly, or reports of suspected adverse reactions in the neonate that are classified as serious.

The female participant or pregnant female partner will be followed to determine the outcome of the pregnancy. The Investigator will collect Follow-Up information on the female participant or pregnant female partner and the neonate, and the information will be forwarded to the Sponsor.

Any post-study pregnancy-related SAE considered reasonably related to the study intervention by the Investigator will be reported to the Sponsor as described in [Section 7.8.2](#). While the Investigator is not obligated to actively seek this information in former study participants or pregnant female partners, they may learn of an SAE through spontaneous reporting.

For pregnant female participants, no further dosing will be permitted.

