### 4.3 Planned Duration of Study

The expected duration of participation for each participant who completes all study visits, from Screening to the EOS visit, is up to 16 weeks. The treatment duration for both Part A and Part B of the study are expected to be the same, as procedures are identical.

- Screening may take up to 28 days.

- The Baseline/Preparatory Period could last up to 4 days and should not be performed >4 days prior to Day 1.
- Enrollment confirmation will take place prior to dosing on Day 1; once enrollment has been confirmed, the Treatment Period will commence.
- The 4-week Treatment Period will consist of four dose sessions 1 week apart, with a telephone visit 1 day after each dose session for collection of safety assessments (AEs, concomitant medications, and C-SSRS) and a follow-up visit to assess safety and efficacy 2 days after each dose session.
- After the final session of the Treatment Period (Visit 14), participants will enter the Follow-Up period. Participants will attend a Follow-Up visit and a Reflection Session approximately 1, 2 and 3 weeks after the final study drug administration, followed by an EOS visit 6 weeks after the final study drug administration. Participants will also be contacted via telephone for collection of safety assessments on Day 57 ( $\pm 2$  days).
- Participants withdrawing before completion of the study should be encouraged to attend a visit that would duplicate the EOS visit to collect safety and efficacy information.

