## **4.6 End of Study**

### **4.6.1 End-of-Study Definition**

The EOS is defined as the date of the last visit of the last participant in the study.

A participant is considered to have completed the study if the participant has completed all periods of the study including the last visit (Day 64).

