### 6.1 Inclusion Criteria

1. Male or female participants aged between 18 to 65 years, inclusive.
2. Participant meets the DSM-5 criteria for current severe PTSD diagnosis, with a symptom duration of at least 6 months at Screening, as assessed by the following psychometric assessments:
  - a. CAPS-5 (past month version).
  - b. Life Events Checklist for DSM-5 (LEC-5).
    - The PTSD diagnosis will be confirmed at Baseline by the central rater.
3. Participant must have a CAPS-5 score of  $\geq 35$  at Screening and  $\geq 28$  at Baseline.
4. Participant has failed at least one treatment for PTSD (either psychotherapy or pharmacological treatment).
5. Proficient in reading and writing in local language sufficient to complete questionnaires.
6. Free from any other clinically significant illness or disease that may adversely affect:
  - a. the safety of the participant, or,
  - b. the integrity of the study (see [Section 6.2](#)).
7. Willing to refrain from taking any psychiatric medications or interventions during the study, unless provided by the Site Investigator.
  - No participant will be asked to discontinue potentially beneficial treatment in order to participate in this study.
8. Willing to provide a contact for emergencies.
9. Willing to be contacted via telephone for all necessary telephone contacts.
10. <Removed in Amendment 3>
11. Males who engage in sexual activity that has the risk of pregnancy must agree to use one of the following acceptable contraceptive methods and agree to not donate sperm throughout the study and for at least 90 days after the last dose of the study medication:
  - a. Use of a double barrier method (male condom with a diaphragm or a cervical cap)
  - b. Female use of hormonal contraceptives (as described below)
  - c. Either partner is surgically sterilized (as described below)
  - d. Abstinence, if consistent with the participants preferred and usual lifestyle

12. Females of childbearing potential\* who are sexually active with a male partner must be willing to use one of the following acceptable contraceptive methods throughout the study and for at least 1 month after the last study drug administration.
  - a. Hormonal contraceptives or intrauterine devices: at least 4 weeks before first dosing and must follow that product's package insert instructions including additional protection at times when hormonal contraceptive doses might be missed

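### Partner pregnancies are collected to an ambiguous end of study, which for some male participants covers only about half of the 90-day contraception period

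*Protocol*

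**What the plan says.** Four parts of the protocol bear on this.

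- **Contraception period for men.** Section 6.1, criterion 11: men whose sexual activity could lead to pregnancy must use an accepted method and "agree to not donate sperm throughout the study and for at least 90 days after the last dose of the study medication".
- **Pregnancy collection.** Section 7.8.3.1 sets a single collection period for women in the trial and for men's partners; pregnancy details for "female partners of male participants will be collected after the start of the study until the end of the study". Sites report within 24 hours of learning of a pregnancy, and it is then followed to outcome.
- **After the study.** The same section keeps pregnancy-related SAEs reportable if the investigator considers them reasonably related. It adds: "While the Investigator is not obligated to actively seek this information in former study participants or pregnant female partners", such an event may come to light spontaneously.
- **When the study ends.** Section 4.6.1: "The EOS is defined as the date of the last visit of the last participant in the study". The same section counts an individual as complete at the Day 64 visit. Section 4.3 describes follow-up visits "followed by an EOS visit 6 weeks after the final study drug administration". The Schedule of Assessments (section 1.3) has no contact after that visit.

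For comparison, criterion 12 asks female participants for contraception "throughout the study and for at least 1 month after the last study drug administration".

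**The concern.** The protocol sets 90 days after the last dose as the period in which a male participant should avoid conceiving. A partner pregnancy in that period is therefore a contraceptive failure or a lapse that the sponsor would want to know about. Section 6.4 already lists a partner's pregnancy among possible reasons for withdrawal or for stopping study drug. Yet the collection rule is tied to the end of the study, not to the last dose, and that term can be read in two ways. On either reading some of the 90 days can fall outside collection. On the whole-trial reading, the amount depends on when a man enrolled and not on his exposure.

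What is at stake is safety information. Section 2.4 counts 51 people formally evaluated on methylone, so each exposed pregnancy is informative. If only related serious outcomes surface after the study, there is no count of exposed pregnancies to set them against.

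**Working it through.** **Inputs**

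- Last planned dose: Day 22, window ±1 day (section 1.3).
- Individual EOS visit: Day 64, window ±3 days (section 1.3).
- Male contraception period: 90 days after the last dose (section 6.1, criterion 11).
- Female contraception period: 1 month after the last dose (section 6.1, criterion 12).

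**Reproducing the plan's own interval.** 64 − 22 = 42 days, and 42 / 7 = 6.0 weeks. This agrees with section 4.3.

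**Reading 1: collection ends at the participant's Day 64 visit.** Uncovered days = 90 − (EOS day − last-dose day).

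| Last dose | EOS visit | Covered | Uncovered | Share uncovered |
|---|---|---|---|---|
| Day 22 | Day 64 | 42 | 48 | 53% |
| Day 21 | Day 67 | 46 | 44 | 49% |
| Day 23 | Day 61 | 38 | 52 | 58% |
| Day 15 (fourth session missed) | Day 64 | 49 | 41 | 46% |

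The 90 days end on Day 22 + 90 = Day 112, which is 48 days after Day 64. A man who leaves at an Early Termination visit soon after a dose would have a larger uncovered share, because fewer days have passed since that dose.

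**Reading 2: collection ends on the trial's last visit (section 4.6.1).** Take a completer with nominal visits whose Day 64 falls D days before that date. Uncovered days = 48 − D, and zero once D is 48 or more. For example:

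- D = 0 (last to finish): 48 days.
- D = 20: 48 − 20 = 28 days.
- D = 48 or more: none.

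Collection is formally open after Day 64 on this reading, but no visit or call is scheduled in which to ask.

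**Female participants.** One month after Day 22 ends at about Day 52 to 53 (22 + 30 or 22 + 31), before Day 64. Collection outlasts their contraception period, so the mismatch concerns male participants' partners only.

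**What remains reportable after the study**

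- Section 7.8.3.1: pregnancy-related SAEs judged reasonably related. It treats spontaneous abortion, congenital anomaly and serious suspected reactions in the newborn as meeting the SAE criterion.
- Section 7.8.1.1: any reasonably related SAE that the investigator learns of, with no time limit after discharge.
- Section 7.8.1.3: serious treatment-related events, whatever their time of onset.

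None of these collects an uncomplicated pregnancy, an outcome judged unrelated, or an event that nobody volunteers.

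**The case against.** The strongest reply is that the only formal end-of-study definition is the whole-trial one. When the protocol wants an individual cut-off it says so: sections 7.8.1.1 and 7.8.1.2 run AE collection to the EOS visit. A reader might infer from the Day 64 arithmetic that every male participant has a 53% gap. The documents do not support that, because under section 4.6.1 anyone who finishes at least 48 days before the trial's last visit is covered for the full 90 days. This part of the reply stands. It does not settle the meaning, however. Footnote 4 of the Schedule of Assessments uses end of study for an individual's visit, and section 7.8.3.1 itself speaks of former participants.

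A reader might also infer that a late pregnancy is neither reported nor followed. That too goes beyond the documents, given the post-study reporting rules in sections 7.8.1.1, 7.8.1.3 and 7.8.3.1. These rules are passive and limited to related serious events, so they narrow the loss without removing it.

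Third, a contraception period and a data-collection period are different rules, and the protocol gives no rationale for the 90 days. This is correct: the two sections do not contradict each other, and calling the 90 days a risk window would be an inference. Aligning the periods is sensible practice, not the repair of an error.

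Lastly, the consent form, the Investigator Brochure and the pregnancy notification procedure are not among the material reviewed. Whether participants are already told to report later pregnancies, and what reproductive data exist, cannot be judged.

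**Conclusion.** The point holds as a minor gap in safety data collection. Section 7.8.3.1 leaves open which end of study applies. For a completer whose collection stops at Day 64, or for the last participant to finish under the whole-trial definition, 48 of 90 days (44 to 52 across both visit windows) lie outside collection. For earlier finishers under the whole-trial definition the gap shrinks to nothing as D approaches 48. About half is therefore the size for these cases and not for all male participants.

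The number of pregnancies affected is likely to be small. Section 9.2 plans 32 participants per arm in Part B. Only men in the methylone arm whose sexual activity carries a pregnancy risk are concerned, and only if contraception fails or is not used. The documents give neither a sex split nor an expected number of pregnancies. The efficacy analysis and the power are untouched.

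The figures assume nominal visits except where a window or a missed session is stated, and they count from the last dose actually taken.

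**What to change.** Reconcile section 7.8.3.1 with criterion 11 and section 4.6.1. For partner pregnancies, replace the end-of-study limit with a per-participant one that uses the protocol's existing period: 90 days after that participant's last dose. Criterion 11 itself stays as it is.

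At the last visit, tell male participants to report a partner pregnancy that arises in that period. This should include men leaving at an Early Termination visit and men entering an extension study. The Exit Plan (section 4.6.2) already supplies a study contact and could carry the instruction, but participants entering an extension need not receive one, so it cannot be the only route. Check whether the consent form already says this, and add it if not.

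The cost is a protocol amendment and possibly a few more pregnancy forms and outcome follow-ups. No additional visit is needed.

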#### 7.7.1.2 *Serious Adverse Event*

An SAE is any untoward medical occurrence that, at any dose:

- Results in death,
- Is life-threatening,

Note: The term 'life-threatening' in the definition of 'serious' refers to an event in which the participant was at risk of death at the time of the event. It does not refer to an event, which hypothetically might have caused death, if it were more severe.

- Requires hospitalization or prolongation of existing hospitalization,

Note: In general, hospitalization signifies that the participant has been detained (usually involving at least an overnight stay) at the hospital or emergency ward for observation and/or treatment that would not have been appropriate in the physician's office or outpatient setting. Complications that occur during hospitalization are AEs. If complication prolongs hospitalization or fulfils any other serious criteria, the event is serious. When in doubt whether 'hospitalization' occurred or was necessary, the AE should be considered serious.

- Results in persistent or significant disability or incapacity,

Note: The term 'disability' means a substantial disruption of a person's ability to conduct normal life functions. This definition is not intended to include experiences of relatively minor medical significance such as uncomplicated headache, nausea, vomiting, diarrhea, influenza and accidental trauma (e.g., sprained ankle) which may interfere or prevent everyday life functions but do not constitute a substantial disruption.

- Is a congenital abnormality or birth defect,
- Is an important medical event.

Note: Medical or scientific judgement should be exercised in deciding whether reporting is appropriate in other situations, such as important medical events that may not be immediately life-threatening, or result in death or hospitalization, but may jeopardize the participant or may require medical or surgical intervention to prevent one of the other outcomes listed in the above definition. These should also be considered serious. Examples of such events are invasive or malignant cancers, intensive treatment in an emergency room or at home for allergic bronchospasm, blood dyscrasias or convulsions that do not result in hospitalization, or development of drug dependency or drug abuse.

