#### **6.2.1.2 Serious Adverse Events**

A SAE is any untoward medical occurrence that, at any dose:

- Results in death
- Is life-threatening
- Requires hospitalization or prolongation of existing hospitalization
- Results in persistent or significant disability or incapacity
- Is a congenital abnormality or birth defect
- Is an important medical event

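### Protocol 7.8.3.1 limits when a pregnancy complication is an SAE in a way that contradicts the general SAE definition, and no section says which rule prevails

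*Protocol*

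**What the plan says.** Protocol 7.8.3.1 says that pregnancy is not itself an AE or SAE, but that "any pregnancy complication or elective termination of a pregnancy for medical reasons will be reported as an AE or SAE". The next sentence limits when that event is serious: "The event meets the SAE criterion only if it results in a spontaneous abortion, congenital anomaly". The sentence goes on to add suspected neonatal reactions, and requires that these are themselves classified as serious.

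The general definition in Protocol 7.7.1.2 opens "An SAE is any untoward medical occurrence that, at any dose" and lists six criteria. Any one is enough. They include death, "Is life-threatening" and "Requires hospitalization or prolongation of existing hospitalization". Its note on hospitalization leans toward inclusion: "When in doubt whether 'hospitalization' occurred or was necessary, the AE should be considered serious". Nothing in the section exempts pregnancy.

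SAP 6.2.1.2 opens "A SAE is any untoward medical occurrence that, at any dose" and gives the same six criteria, again without a pregnancy exception. Protocol 7.8.1.3 requires every AE to be assessed against the 7.7.1.2 criteria.

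**The concern.** The general rule and the pregnancy rule classify the same maternal event differently. The pregnancy rule sits under a heading for special considerations and is worded as a closed list, so a site could reasonably take the specific rule to override the general one. Part B may run at up to about 25 sites, which need to classify such an event in the same way.

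The following depend on the SAE label:

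- the 24-hour report to the Medical Monitor (Protocol 7.8.2);
- the expectedness assessment for SUSARs (the paragraph after Protocol 7.8.2.1);
- the separate SAE listing and the serious-TEAE row (SAP 8.4.1);
- the route in 7.8.3.1 for reporting related pregnancy SAEs that arise after the study.

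**Working it through.** The plan states no figure on this point. The check sets the rules side by side.

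**Step 1: what the restrictive sentence governs.** Its subject is the event named in the sentence before it, which is any pregnancy complication or medically indicated termination. It is therefore not confined to fetal or neonatal outcomes.

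**Step 2: whose events are in conflict.** Protocol 7.7.1.1 defines an AE as an occurrence in a study participant. The direct conflict therefore concerns female participants, not partners of male participants.

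**Step 3: apply both rules to a female participant.** In the first three rows, none of the three listed outcomes occurs.

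| Event | Protocol 7.7.1.2 and SAP 6.2.1.2 | Protocol 7.8.3.1 |
|---|---|---|
| Complication that is fatal or life-threatening | SAE | Not an SAE |
| Complication or medically indicated termination that needs hospitalization | SAE | Not an SAE |
| Complication that is disabling or an important medical event | SAE | Not an SAE |
| Spontaneous abortion meeting no general criterion | Not an SAE | SAE |
| Congenital anomaly | SAE | SAE |

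The first three rows are the contradiction. The fourth shows that the pregnancy list also adds something the general definition does not guarantee, so deleting it would lose coverage.

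**Step 4: look for a rule of precedence.** Protocol 7.8.1.3 points to 7.7.1.2 for every AE. Protocol 7.8.3.1 neither refers to 7.7.1.2 nor says that it replaces it. The SAP never refers to 7.8.3.1. The conflict is unresolved.

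**Step 5: reach into the tables.** SAP 8.4.1 counts an AE as treatment-emergent up to 7 days after the last dose, or later if suspected to be drug-related. On the nominal schedule the last dose is on Day 22, so the window closes on Day 22 + 7 = Day 29. Follow-up runs to Day 64, which leaves 64 − 29 = 35 days in which a new event not suspected to be related stays out of the serious-TEAE row under either rule. A participant found to be pregnant receives no further dose (Protocol 4.8 item 4 and 7.8.3.1), so her window can close sooner.

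**Step 6: reach into the pause rules.** Protocol 4.9 item 10 needs treatment-related SAEs in three participants. Item 11 needs the same SAE in two participants. A maternal event counts only if it meets one of those conditions.

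**The case against.** The strongest reply is that the general definition governs anyway. Protocol 7.8.1.3 sends each AE to it, 7.7.1.2 resolves doubt about hospitalization toward seriousness, and the SAP applies its own definition. This stands to the extent that a reader should not infer that the documents settle a life-threatening or hospitalized maternal event as non-serious. They leave it unresolved, and a site working from 7.7.1.2 would report it correctly. It does not remove the contradiction, because nothing tells a site to prefer that section.

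A second reply is that all three listed outcomes concern the pregnancy, fetus or newborn, so the sentence may only say when a pregnancy outcome is itself an SAE. That may have been the intention, but the text does not support it: the sentence refers back to any pregnancy complication.

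A third reply is that the sponsor would hear of the case regardless. Every pregnancy is reported within 24 hours and followed to outcome, the complication would still be listed as an AE, the DSMB reviews AEs, and 4.9 item 1 allows a pause without an SAE label. All of this stands. The 24-hour report, however, gives notice of the pregnancy. A complication that arises later has its own 24-hour clock only if it is classed as an SAE.

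**Conclusion.** The contradiction is real, and following 7.8.3.1 gives the wrong classification under the plan's own SAE definition. Its practical size is small. Contraception is required, and a negative pregnancy test is needed before each dose. The documents give no pregnancy rate; 0 to 1 pregnancies among the 64 Part B participants is an assumption. The main exposure is the expedited report, the SUSAR assessment and the SAE listing. Efficacy analyses are untouched, and safety analyses are descriptive.

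A reader might infer two larger consequences that the documents do not support:

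- **A shift in the serious-event rate.** One event in an arm of 32 is 1/32 = 3.1 percentage points, but this reaches the serious-TEAE table only if the event falls within the 7-day window or is suspected to be related.
- **A step toward a pause for each event.** Items 10 and 11 of 4.9 require treatment-relatedness or the same SAE in two participants. With 0 to 1 pregnancies, pregnancy events alone could not meet item 11.

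**What to change.** Reconcile the sections by replacing the restrictive sentence in Protocol 7.8.3.1 with wording such as:

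> A pregnancy complication or medically indicated termination is an SAE if it meets any criterion in Section 7.7.1.2. In addition, spontaneous abortion, congenital anomaly and serious suspected adverse reactions in the neonate are always reported as SAEs.

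This keeps everything 7.8.3.1 now captures and brings it into line with 7.7.1.2, 7.8.1.3 and SAP 6.2.1.2. The SAP needs no change. The cost is one sentence in a protocol amendment and at most an occasional extra SAE form.
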